Each of these benchmarks was met or exceeded in our trial. First, we invited 17 providers to participate with the goal of recruiting at least 10 providers who referred eligible families to the study: 6 were based in child advocacy centers; 11 were based in state mental health facilities. All 17 providers consented, and 13 (76.5%) actively participated by referring and treating study families. Of the remaining 4 providers, 2 did not actively engage with the research team (i.e., did not respond to brief, weekly e-mail communications), and 2 indicated that they did not

have any appropriate cases to refer during the 4-month recruitment period. Second, we exceeded our goal of recruiting 20 families into the feasibility trial. A total of 31 families were referred to the study during our 4-month recruitment window; **24 of these families were referred within 2 months**, which led us to close recruitment early for several providers. Third, although participation rate was not explicitly proposed as a benchmark, it is notable that 27 of the 31 families (87.1%) referred by providers were consented and enrolled successfully into the study by our research team. Of these, only one family (3.7%) declined session audiorecording. Fourth, TF-CBT was completed (i.e., ≥ 6 sessions) by 88.9% of families. Fifth, we exceeded our goal of retaining $\geq 70\%$ of families through post-treatment assessments. Fully 24 of 27 families were retained for mid-treatment assessments (88.9%), and we completed post-treatment assessments with 21 of 27 (77.8%). Sixth, we estimate that 247 TF-CBT sessions were completed for the 26 families that consented to audiorecordings. Of these, we received 221 audiorecordings (89.5%). Moreover, more than half of the audiorecordings we did not receive were accounted for by one provider. The remaining 12 providers adhered $\sim 95\%$ to audiorecording and uploading procedures. Seventh, coder agreement for **child engagement** was excellent (ICC $M=0.81$; range: 0.60-1.00) and coder agreement for **provider fidelity** was outstanding (ICC $M=0.97$). Eighth, all 11 tablet TF-CBT chapters were used with at least 5 families assigned to providers in the tablet TF-CBT condition; some chapters were used much more extensively than others (e.g., What Do You Know?).

D. RESEARCH DESIGN AND METHODS (including data analysis)

D1. Overview

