All measures were chosen because they are well-established instruments that are well validated and sensitive to treatment gains (e.g., K-SADS-PL). Assessments will be administered at baseline and 3, 6, 9, and 12 months post-baseline. Treatment fidelity and child engagement will be measured by coding videorecorded sessions with established observational coding schemes. In our NIMH R34, sessions were audiorecorded; only 1 of our 27 participating families declined audiorecording. Moreover, families reported in post-study interviews that videorecording was an acceptable alternative. Audiorecordings were optimal for coding of fidelity in our pilot study, and were satisfactory in coding child engagement. However, there were instances in which disagreement occurred in child engagement ratings due to ambiguous interactions between children and providers that will be

clearer with video feedback. For these reasons, we will seek consent to videorecord sessions, but will offer audiorecording (which was accepted by 96% of our pilot-study families) as an alternative if families express discomfort with videorecording.

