examine the potential increase in engagement across cases due to practice.

D8c. Hypothesis 3: Greater improvement in clinical outcomes will be observed at post-baseline assessments among children receiving tablet-facilitated TF-CBT vs. standard TF-CBT. Response to the intervention will be evaluated with a piecewise longitudinal MLM that contains 3 levels. Level-1 will correspond to measurement period, level-2 to child, and level-3 to provider. The primary outcome for Hypothesis 3 will be scores on the K-SADS-PL, UCLA PTSD Index, CDI, and CBCL. A piecewise model allows for separate change trajectories to be estimated for distinct periods of time. Patients are expected to show more rapid change during treatment than during follow-up (roughly corresponding to 9- and 12-month post-baseline period). The level-1 model will include a fixed effect for pretreatment (intercept), rate of change during treatment, and rate of change for the follow-up period. Time varying covariates (level-1) will be added to the model based on a theoretical rationale and changes in model fit. The level-2 model will account for child level covariates, including comorbid symptoms and trauma history. The level-3 model will include a dichotomous fixed effect representing the condition to which each provider was randomized (tablet-facilitated vs. standard TF-CBT). Of interest is the cross-level interaction between rate of change during treatment and the condition to which the provider was assigned. Cross-level interactions between the rate of change during follow-up also will be examined.

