D8d. Hypothesis 4 and 5: Provider fidelity (hypothesis 4 target) and child engagement (hypothesis 5 target) will mediate the relation between study condition and mental health outcomes. The proposed design is consistent with an enhancement mediation design¹³³ to determine if provider fidelity and child engagement are the mechanisms by which tablet-facilitated TF-CBT reduces psychopathology. Enhancement designs evaluate mediation by experimentally manipulating a variable that enhances the effect of the mediator when direct experimental control of the mediator is not possible.¹³⁴ These mechanistic hypotheses will be tested with established guidelines for multilevel mediation¹³¹. Significance is determined by a product of coefficients test with asymmetric bootstrapped SEs and 95% CIs for the product. This requires estimation of two paths: the effect of tablet-facilitated TF-CBT on engagement and fidelity (a-paths); and the effect of engagement and fidelity on outcomes, controlling for the effect of tablet TF-CBT (b-paths). The mediation effect is estimated by the product of the fixed effect coefficients for the a- and b-paths. A Monte Carlo method is used to create a 95% confidence interval to test for the mediated effect as this effect does not assume a normal distribution. Provider fidelity and child engagement will be evaluated in separate models. Tests for mediated effects are associated with a number of challenges and assumptions such that a single study typically cannot address and overcome each of them.¹³³⁻¹³⁴ As emphasized by MacKinnon and colleagues, the proposed randomized design is a relative strength that strengthens conclusions about the mediated effects. The mediation hypothesis will first be evaluated using all time points. If supported, follow-up analyses in which mechanism measures obtained from the first half of treatment will evaluate change in psychopathology in the second half of treatment. This two stage procedure will support the causal sequence of mediation - that an initial change in the mediator is associated with a reduction in psychopathology.¹³⁴ Combined, the proposed mediation model will provide important preliminary evidence to support, or reject, therapist fidelity and child engagement as potential mediators of the effect of iTF-CBT on child outcomes.

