Drs. [name], [name], [name], or [name] will travel to each partnering site to meet with providers to explain study procedures and obtain written informed consent from interested providers prior to initiating data collection. ***Participating providers will be assigned randomly to the standard TF-CBT condition or the tablet-facilitated TF-CBT condition.*** Randomization will occur immediately after enrollment of providers' first study-eligible family. All participating providers will already have been trained in the TF-CBT model as evidenced by their prior participation as a trainee via *Projects BEST* and *PATS*. Providers assigned to the tablet-facilitated TF-CBT condition will receive additional training (approximately 50 minutes in length) in the navigation of the app and use of its tailoring features. The TF-CBT model is designed to be completed over approximately 12 weekly sessions. Provider consent for the clinical trial will include agreement to (1) refer up to 5 cases to the study to maximize the likelihood that treatment is completed with at least 3 study cases per provider, (2) video-record (or audio-record, if preferred by the patient) treatment sessions for families who consent (consent is completed by the study team, not the provider), and (3) complete a brief self-report assessment battery at the beginning and end of study participation. We did not explicitly require use of the tablet TF-CBT resource for providers in our NIMH R34 pilot study. Rather, we encouraged use and invited a flexible approach to using it. For this study we will follow the same procedure by explicitly conveying to providers that they are free to use or not use the app – or any activity within – as they wish with study families. As mentioned above, in our pilot study, most of the tablet TF-CBT chapters were used by the vast majority of providers, and they reported finding it useful in teaching skills to the patients and keeping them on protocol. Videorecording of sessions is one additional role of participating providers, but this action is standard and typical in clinical practice for trainers or supervisors to review session recordings. In fact, session recordings were used for many of these same providers when initially receiving training and ongoing consultation in TF-CBT via MUSC's dissemination initiatives, led by two of our study collaborators (Drs. [name] and [name]). Families who express discomfort around video-recording of treatment sessions will be offered an alternative for sessions to be audio-recorded. Video-recording is preferable because we found in our pilot study that it will assist our coders in interpreting ambiguous interactions when rating children's engagement via behavioral coding (in contrast, it would likely have a negligible impact on coding of fidelity). However, we also found that adequate coder agreement was achieved and maintained with the use of audio-recordings in our pilot, and therefore we

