Assessment Procedures. As described in the research plan, families will complete assessments conducted by study staff at baseline, and at 3-, 6-, 9-, and 12-months post-baseline. The assessments will be conducted via telephone for several reasons. First, in-person interviews are cost prohibitive because we are recruiting families from a large geographic area across three states. Second, it would also be cost prohibitive to arrange televideo post-baseline assessments with all families. We believe that scheduling a small number of baseline interviews for new patients in collaboration with partnering clinics will be a challenging but manageable process, and we already have taken several steps toward identifying these processes with these clinics. However, it is impractical and cost prohibitive to coordinate 1,800 assessments (5 assessments x 360 participants) with our partnering clinics throughout the course of the study. Third, efforts to coordinate televideo assessments through the

clinics for all 1,800 assessments would have clear adverse effects on study retention because this would increase burden associated with transportation and time for families. Fourth, research has shown that telephone assessments are acceptable and methodologically appropriate for children as young as 8 years old, which corresponds to our lower age range for children recruited into the study. Taken together, the use of telephone methodology for post-baseline assessments will ensure that study costs, data quality, retention of participants, and burden to families associated with scheduling and transportation are all manageable and reasonable within the scope of the proposed study.

Although unlikely, should an individual become uncomfortable during the assessment, the interviewer will provide assistance or direct families to other sources of support. Many victims of crime and other traumatic events rarely report that being asked about their traumatic events is distressing. Zajac et al (2011) reported findings from a nationally representative sample of 3,614 adolescents who completed telephone-based surveys asking about exposure to physical and sexual assault, community and domestic violence, or other serious accidents. Only 5.7% of the youth interviewed found any of the interview upsetting, of which only 0.2% remained upset at the time the phone interview concluded. Only 2 (<0.1%) participants were upset enough to want to speak with a counselor at the conclusion of the interview.

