
obtained from the first half of treatment will evaluate change in symptomatology in the second half of treatment. Combined, the proposed mediation model will provide important evidence to support, or reject, therapist fidelity and child engagement as potential mediators of the effect of SPARK on child outcomes.

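### The mediation follow-up step needs symptom change in the second half of treatment, but the plan does not tie the halves to assessment visits, and a promptly started 12-week course would leave that change unobserved

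*Protocol*

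**What the plan says.** Hypotheses 4 and 5 propose that provider fidelity and child engagement mediate the effect of the toolkit on child outcomes. Protocol D8d tests this in two stages. The first uses all time points. If it supports mediation, a follow-up analysis is run in which "mechanism measures obtained from the first half of treatment will evaluate change in psychopathology in the second half of treatment". The protocol gives the reason: "This two stage procedure will support the causal sequence of mediation". SAP 2.9.1 keeps the follow-up step, with measures "obtained from the first half of treatment will evaluate change in symptomatology in the second half of treatment", but not that sentence.

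The timing information is spread over several sections:

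- **Symptom assessments.** Protocol D4g: "Assessments will be administered at baseline and 3, 6, 9, and 12 months post-baseline". No other symptom occasion is named. The weekly provider portal in D4e is described as taking activity reports and session uploads, not symptom scores.
- **Treatment length, first description.** Protocol E.1.a, Provider Recruitment: "The TF-CBT model is designed to be completed over approximately 12 weekly sessions".
- **Treatment length, second description.** Protocol D8c expects "more rapid change during treatment than during follow-up (roughly corresponding to 9- and 12-month post-baseline period"). SAP 2.9.1 says the same. This leaves the 3- and 6-month visits in the treatment phase. Protocol E.1.a, Child/Family Recruitment, also describes some of the assessments as falling during therapy.
- **Mediators.** Both are coded session by session (D4h, D4i) and then aggregated per child. D8a describes the fidelity score as covering the whole case and as suited to use as a mechanism; D8b takes the same approach to engagement.

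**The concern.** To show that the mediator moved before symptoms did, the analyst needs a symptom score near the middle of treatment, or at least a symptom interval that begins after the mediator was measured. The plan speaks of halves of treatment, but the visits are fixed by months from baseline, and nothing links the two. Whether the step can be done therefore depends on how long treatment lasts and when it starts. The documents describe the length in two ways and give no interval from baseline to first session.

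Two things are at stake. In a short course, the only available change runs from baseline to 3 months and overlaps the period in which the mediator is rated, so children who improve early and then engage more would look like mediation. In a long course, a mediator averaged over the whole case contains sessions that took place after some of the outcomes it is used to explain. Undefined halves also leave the analyst free to choose the interval after seeing the data.

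**Working it through.** **Plan's own count.** Protocol E.2.b (Assessment Procedures) gives 1,800 assessments for 360 participants. 5 × 360 = 1,800, which reproduces the figure and confirms five symptom occasions per family.

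**Visits in weeks.** One month = 365.25 / 12 / 7 = 4.348 weeks. The visits are at weeks 0, 13.04, 26.09, 39.13 and 52.18.

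**Course in weeks.** Let L be the lag in weeks from baseline to first session, and g the spacing in weeks. For 12 sessions, the last is at L + 11g and the midpoint at L + 5.5g. The position of the 3-month visit in the course is (13.04 − L) / 11g; a value above 1 means after the last session. L and g are assumptions, because the documents give neither a start lag nor a delivered spacing.

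| g | L | Last session (week) | Midpoint (week) | Position of 3-month visit |
|---|---|---|---|---|
| 1 | 0 | 11 | 5.5 | 1.19 (after the end) |
| 1 | 2 | 13 | 7.5 | 1.00 (just after the end) |
| 1 | 4 | 15 | 9.5 | 0.82 |
| 1.5 | 0 | 16.5 | 8.25 | 0.79 |
| 2 | 2 | 24 | 13 | 0.50 |

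**Thresholds.** With weekly sessions, the 3-month visit falls inside the course only if L exceeds 13.04 − 11 = 2.04 weeks. It sits at the midpoint only if L is 13.04 − 5.5 = 7.54 weeks. With no lag, it falls inside only if g exceeds 13.04 / 11 = 1.19 weeks.

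**Pilot.** Protocol C5: "we estimate that 247 TF-CBT sessions were completed for the 26 families that consented to audiorecordings". 247 / 26 = 9.5 sessions per family. This is a count and does not give duration. If those sessions were weekly with no lag, the last would be at week 8.5.

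**Course of about 6 months.** If treatment runs from baseline to week 26.09, the midpoint is 26.09 / 2 = 13.04, which is the 3-month visit. Change from 3 to 6 months is then second-half change. With evenly spaced sessions, about half of those in a whole-case aggregate come after the 3-month outcome.

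**Intermediate case.** With weekly sessions starting at week 4, sessions run from week 4 to week 15. The 3-month visit is 82% of the way through, well past the midpoint, and 2 of the 12 sessions (weeks 14 and 15) follow it.

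**The case against.** A reader might infer that no symptom assessment falls inside treatment and that temporal order cannot be tested at all. The documents do not support that. The 12-session figure describes how the model is designed, not how long delivery takes. D8c and SAP 2.9.1 put the 3- and 6-month visits in the treatment phase, and E.1.a describes some assessments as falling during therapy. A start lag just over 2 weeks, or spacing above about 1.19 weeks, is enough to put the 3-month visit inside the course. A lag is plausible for a provider's first case, since randomization follows that family's enrollment and tablet providers then need about 50 minutes of extra training. Even in a prompt 12-week course, first-half ratings still precede the 3-month score. What is lost is the separation of second-half from first-half change, and adjustment for symptoms at mid-course.

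A reader might also infer that one of the two stages must fail whatever the treatment length. That goes too far as well. With a course of about 6 months, the follow-up step can be estimated. D8d gives the causal-sequence role to the procedure as a whole and does not claim that the first stage establishes order by itself. The overlap between a whole-case mediator and the 3-month outcome weakens that stage but does not make it uninterpretable.

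Finally, the step is conditional on the first stage, and the protocol calls the mediation evidence preliminary and acknowledges that one study cannot meet every mediation challenge. The SAP omits the causal-sequence sentence, though it also drops the word preliminary.

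These points remove the absolute claims. They leave the central one: the interval that the step depends on is undefined, and under the length stated in E.1.a with a prompt start it is not observed.

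**Conclusion.** The point holds in conditional form. If treatment is delivered as about 12 weekly sessions and starts within about 2 weeks of baseline, no symptom assessment falls inside the course, the follow-up step cannot be carried out as written, and reverse causation from early improvement cannot be excluded. If treatment runs to about 6 months, the step can be done but rests on the single 3-to-6-month interval, while a whole-case mediator in the first stage would draw about half its sessions from after the 3-month outcome. That fraction assumes even spacing and that the D8a and D8b aggregates are the first-stage mediators, which D8a indicates for fidelity but D8d does not restate. Between these cases, a near-weekly course usually places the 3-month visit late, not at the midpoint.

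The documents do not say which case applies. The consequence is confined to Hypotheses 4 and 5 and the causal wording attached to them; Hypotheses 1 to 3 are unaffected. It should be corrected, because mediation is a stated hypothesis with its own power statement in D8h, and the correction is inexpensive.

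**What to change.** 1. Reconcile the treatment-length descriptions in Protocol E.1.a with those in D8c and SAP 2.9.1.
2. For each outcome visit, form the mediator only from sessions held before that visit. For visits after a child's last session this equals the whole-case aggregate, so only visits during treatment are affected.
3. Replace the reference to the second half of treatment with named visits, and define the first half in advance. Two relations serve: first-half mediator with 3-month symptoms adjusted for baseline; and mediator from sessions before the 3-month visit with 3-to-6-month change, adjusted for 3-month symptoms.
4. Limit the causal-sequence sentence to what these intervals can show. State that in a 12-week course the 3-to-6-month change is change after treatment, and that baseline-to-3-month change overlaps the mediator period. Carry the same caution into the SAP.

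The cost is some extra analysis work and a mediator based on fewer sessions (6 of 12 for the first half of a full course), hence noisier. No new assessment is needed. The rule does depend on session dates. Weekly reporting and uploads in D4e imply that they are held, but the text does not say so, and the form for mailed recordings lists file name, session type and initials only. Their capture should be confirmed before the rule is adopted.

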We will evaluate the cost-effectiveness of tablet-facilitated TF-CBT vs. standard TF-CBT using methods outlined by Hargreaves.¹³⁴ We will collect data on the incremental cost that access to the tablet toolkit adds to standard TF-CBT. Costs include the cost of training providers in the use of tablet TF-CBT, cost of any study personnel time needed to address providers' needs while using the tablet (these were minimal in the pilot), or additional time of existing personnel for using the tablet TF-CBT toolkit (e.g., setup, tailoring activities). It also will include additional supplies, equipment, or overhead costs associated with providing tablet-facilitated TF-CBT vs. standard TF-CBT. Further, it will include technology-related costs associated with maintaining the app over time. The value of additional mental health provider time in tablet-facilitated vs. standard TF-CBT will be valued at the mean 1-hr cost of a provider based on estimates provided by the US Department of Labor Statistics. We will note the cost of development of tablet TF-CBT as well as other exclusive research costs, but because these are one-time development and research costs that will not be replicated in other facilities, we will exclude them from cost-effectiveness and cost-benefit analyses. We will define benefits as the difference in cost of health services utilization in the event tablet-facilitated TF-CBT reduces the number of sessions a provider needs to achieve the desired clinical outcomes. We will estimate an incremental cost-effectiveness ratio as: [(cost of tablet TFCBT - cost of TFCBT) divided by (effectiveness of tablet TF-CBT - effectiveness of standard TF-CBT)]. Effectiveness will be measured based on children's mental health outcomes. This ratio will estimate the increased average cost needed to gain an average of 1 point of improvement per time period in the target clinical outcome. We will examine differences in means, medians, and quartiles of cost by tablet-facilitated relative to standard TF-CBT using the appropriate tests based on the distribution of the cost variable. We will use generalized linear models with the appropriate distribution to examine the association of receiving the tablet TF-CBT with mental health session treatment costs, adjusting for patient demographics. We also will conduct a sensitivity analysis by estimating different cost models while adjusting for the clinical outcomes as we have done elsewhere.¹³⁵ We will do the same for mental health services utilization using a count model (Poisson or Neg Bin if overdispersion is encountered or zero-inflated if many zeros are present). As in the case of the clinical outcome analyses, random and fixed effects models will be estimated to account for clustering at the provider level.

E. PROTECTION OF HUMAN SUBJECTS

